 - 13 Imaging (CT or MRI for CNS tumours or soft tissue lesions) assessment is to be performed every 8 weeks until progression of disease. In case of objective response, the latter has to be confirmed 4 to 6 weeks after initial OR observation. Consecutive imaging assessment will be performed every 8 weeks. In exceptional cases when patients have been stable on treatment for at least 2 consecutive images (i.e. 16 weeks), imaging intervals may be extended to 12 weeks upon discussion between the investigator and the sponsor.
 - 14 Tumour marker(s) in urine or blood as indicated depending on tumour type (e.g. catecholamines (VMA/HVA, dopamine), NSE in neuroblastoma)
 - 15 Intra-patient dose escalation might be allowed as soon as the next higher dose tier is completed and considered safe (applicable to dose finding part only). A dose reduction can also be applied in case of drug-related toxicity (see [Section 4.1.4.3](#))
 - 16 New kit(s) of trial drug must be dispensed at visit 1 of each course. If needed (e.g. in case a dose adaptation has to be applied during treatment course), new kit(s) of trial drug might be dispensed outside of the planned visit schedule
 - 17 A full PK profile (extensive PK sampling) is to be taken at course 1, day 1: pre-dose before afatinib administration then 1h, 2h, 3h, 4h, 5h, 6h, 8h and 24h after administration and to be repeated at steady state on day8. In exceptional cases where extensive PK sampling is not possible, a limited sampling approach must be applied with blood sampling before, 1h and 3 h after afatinib administration. An additional trough sample is to be taken on day 15 to confirm steady state exposure to afatinib. In addition, trough CSF sampling (from Rickham, Ommaya reservoirs or from lumbar puncture performed for clinical reasons not related to the trial) may be taken on day 8 or later. This CSF sampling is optional. Each trough CSF sample has to be accompanied by a trough plasma sample taken at the same time-point. For further details on time points and sampling volumes, see [Section 5.5.2](#) and [Appendix 10.3](#).
 - 18 During the dose escalation part, a DLT confirmation fax has to be sent to the sponsor before start of course 2.
 - 19 AE/SAE after the 28-30 days FU period have to be reported only if considered relevant by the investigator.
-
- 22 Lansky for patients ≤ 12 years or Karnofsky for patients older than 12 years at time of informed consent

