Blood sampling for safety lab	
Blood collection for assessment of the parameters as described in Section 5.2.3. In case the safety lab parameters as outlined in Section 5.2.3 have been collected within the past 7 days prior signing informed consent, the data may be reported in the eCRF and no new blood needs to be collected during screening

Assessment of the tumour disease	
Depending on the tumour type, an assessment of the tumour disease has to be reported in the eCRF based on:
 
 imaging findings tumour markers in blood or urine if indicated bone marrow if indicated 
Tumour assessment does not need to be repeated at the screening visit if there are valid results available from assessments which were performed as part of routine clinical practice within the allowed time window (within 28 days prior to start of treatment).

Tumour tissue	
-Dose finding part: confirm tumour tissue availability for retrospective biomarker testing or provide evidence of ErbB pathway deregulation -MTD expansion cohort: provide tumour tissue for prospective biomarker testing of ErbB pathway deregulation – see Section 5.6

Concomitant therapies	See Section 4.2.1
Adverse events	All AEs occurring since the signature of the informed consent - See Section 5.2.2
Dose assessment	Confirmation of dose according to dose level and BSA

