Visit 1 (day 1)

This visit should take place at day 29 from start of treatment and should serve for confirming patient's eligibility for treatment continuation

- Depending on the patient status, the investigator has to perform a disease assessment on patient's eligibility for the next treatment course. This might include but is not limited to:
 - Imaging findings (requested only every 2 courses: course 3 visit1, C5V1, C7V1...)
 - Tumour markers in blood or urine if indicated
 - Bone marrow if indicated

In case treatment discontinuation is required at this visit, please complete the EOT visit instead of this visit.

For patients included in the dose escalation part, a DLTs evaluation should be provided before to start a new course of treatment.

C2V1 visit should include:

Patient acceptability	Completion of acceptability questionnaires by patients, parents/caregiver and investigator/site staff Special note: at any time, if the patient switches from his/her initial formulation to the other, the questionnaires should be completed again after 28 days of intake of the new formulation.
Quality of life questionnaire	For MTD expansion cohorts/Phase II part only
Repeated procedures	Physical examination and vital signs; weight; blood sampling for safety lab; update on concomitant therapies and adverse events
Performance score	Lansky for patients ≤ 12 years or Karnofsky for patients older than 12 years at time of informed consent
Cardiac assessment	LVEF echocardiography shall be performed and the results must be documented in source data and eCRF for DLT evaluation
Patient diary	Check for completion
Compliance check	Check on trial drug compliance
Eligibility for treatment continuation	Confirm eligibility for further treatment
If the patient eligibility for further treatment is confirmed:	
Dose assessment	Assess appropriateness of the afatinib dose
Dispense trial drug	New afatinib kit(s) must be dispensed to the patient/parent(s)/legal guardian

Proprietary confidential information.

© 2017 Boehringer Ingelheim International GmbH or one or more of its affiliated companies. All rights reserved.

This document may not - in full or in part - be passed on, reproduced, published or otherwise used without prior written permission.

	(recalculate BSA for allocation of dose) for a daily drug intake along this treatment course
--	--

Visit 2 (day 15)

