5.2.2 Secondary endpoint(s)

Dose finding part:

- **Objective response** (OR) assessed by investigator according to the institutional response evaluation criteria for the given tumour type, assessed every 8 weeks until progression of disease
- **Pharmacokinetics** (AUC_{0-24} , C_{max} , $t_{max(ss)}$ and accumulation (or effective) half-life)

MTD expansion cohort part:

- **Progression free survival** (PFS) is defined as the duration of time from the date of first drug administration to the date of the first documented disease progression evaluated according to institutional response criteria or to the date of death from any cause, whichever occurs first. Censoring rules and dates of outcome for PFS under difference scenarios are specified in [Table 5.2.2: 1](#).
- **Duration of objective response** (DoR) is defined as the time from first documented response of CR, VGPR, PR, or MxR until the earliest of disease progression or death among patients with objective response. Censoring rules and dates of outcomes follow the same specifications as for PFS in Table 5.2.2: 1 for applicable scenarios.
- **Pharmacokinetics** ($AUC_{\tau(ss)}$, $C_{max(ss)}$, $t_{max(ss)}$ and accumulation (or effective) half-life)

Table 5.2.2: 1 Censoring rules and determination of date of event or censoring for PFS

Situation	Outcome (event or censored)	Date of outcome
No baseline radiological assessment (no death before second scheduled radiological assessment)	censored	Date of first treatment administration
Death without progression. At most one missed radiological assessments, i.e. at most 112 days between death and last assessment (or treatment start date if no post-baseline assessments).	event	Date of death
Death without progression. Two or more missed radiological assessments, i.e. longer than 112 days between death and last assessment (or treatment start date if no post-baseline assessments).	censored	Date of last radiological assessment / Date of first treatment administration if no post-baseline assessments
No radiological assessment performed post-baseline, vital status is unknown or patient is known to be alive	censored	Date of first treatment administration
Progressed according to radiological assessment. At most one missed radiological assessments, i.e. at most 112 days between progression and last assessment before progression.	event	Date of radiological assessment of progression

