Progressed according to radiological assessment, i.e. longer than 112 days between progression and last assessment before progression.	censored	Date of last radiological assessment before progression
Alive and not progressed (irrespective of missed radiological assessments)	censored	Date of last radiological assessment
Initiation of subsequent anti-cancer therapy		
Subsequent anti-cancer therapy started before progression or death	censored	Date of last radiological assessment before subsequent anti-cancer therapy
No baseline and/or post-baseline imaging and subsequent anti-cancer therapy started prior to a death	censored	Date of first treatment administration

For further details on endpoints, please see CTP Section 5.

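### The PFS table equates one missed scan with 112 days; this fails on the 12-weekly imaging the protocol permits and leaves no tolerance on 8-weekly imaging

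*SAP*

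**What the plan says.** **SAP Table 5.2.2:1 (section 5.2.2).** A radiological progression is an event if "At most one missed radiological assessments, i.e. at most 112 days between progression and last assessment before progression". The matching censoring row gives only the day limit: "Progressed according to radiological assessment, i.e. longer than 112 days between progression and last assessment before progression". The outcome is then dated at the last scan before the progression. Deaths follow the same limit. A death is censored under "Two or more missed radiological assessments, i.e. longer than 112 days between death and last assessment", and the death rows add a fallback reference: "or treatment start date if no post-baseline assessments". The progression rows have no such fallback. Section 5.2.2 applies the same table to DoR where its scenarios fit.

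**Protocol imaging schedule.** Flow Chart footnote 13 sets imaging every 8 weeks. Section 6.2.2 places it at visits, "requested only every 2 courses: course 3 visit1, C5V1, C7V1". For exceptional patients who have been stable on at least two consecutive images, footnote 13 adds that "imaging intervals may be extended to 12 weeks upon discussion between the investigator and the sponsor". It also adds a scan for responders: "In case of objective response, the latter has to be confirmed 4 to 6 weeks after initial OR observation". The Flow Chart gives day 1 of each course from course 2 a ±2-day window. No separate window is given for imaging.

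**Protocol section 5.1.1.2** defines PFS by first documented progression or death from any cause. It contains no rule on missed scans.

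**The concern.** The table joins a count of missed scans to a number of days as if each were a restatement of the other. The day limit is exactly two 8-week intervals. It has no allowance for visit windows or for the longer interval the protocol permits. Wherever the real schedule departs from an exact 8-week grid, the wording and the day limit can classify the same event differently.

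At stake is whether a documented progression or death counts. When the day limit is exceeded, the event disappears from the Kaplan-Meier estimate and the patient's follow-up ends at the previous scan. The MTD expansion/Phase II part plans up to 38 evaluable patients, so a few such cases could be visible in the curve. The patients eligible for 12-weekly imaging have been stable for at least 16 weeks, so they are also among those with longer PFS times.

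**Working it through.** **Inputs.** Standard interval 8 weeks = 56 days; permitted interval 12 weeks = 84 days (footnote 13). Course length 28 days (Flow Chart). Visit window ±2 days (Flow Chart), *assumed* to apply to scans. Limit 112 days (SAP Table 5.2.2:1).

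**Step 1. The plan's own figure.** One missed scan, progression at the next: 2 × 56 = 112 days. The limit is reproduced, and on an exact 8-week grid the two tests agree: 0, 1 or 2 misses give 56, 112 or 168 days.

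**Step 2. Add the window.** For a progression found at the next scheduled scan after *m* consecutive misses, gap = (m + 1) × interval + b − a. Here a and b are the deviations of the earlier and later scan, each from −2 to +2 days.

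| Schedule | Missed | Nominal | With ±2 days | By the words | By 112 days |
|---|---|---|---|---|---|
| 8-weekly | 0 | 56 | 52–60 | event | event |
| 8-weekly | 1 | 112 | 108–116 | event | event to 112, censored 113–116 |
| 8-weekly | 2 | 168 | 164–172 | censored | censored |
| 12-weekly | 0 | 84 | 80–88 | event | event |
| 12-weekly | 1 | 168 | 164–172 | event | **censored** |
| 12-weekly | 2 | 252 | 248–256 | censored | censored |

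*8-weekly, one miss.* The gap exceeds 112 when b > a. Of the 5 × 5 = 25 date pairs, 4 + 3 + 2 + 1 = 10 do so. This counts date combinations and is not a share of patients.

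*12-weekly, one miss.* All 25 pairs exceed 112. The nominal 168 days already does so without any window assumption.

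**Step 3. Deaths on 12-weekly imaging.** The second scan falls due at 164 to 172 days. A death on days 113 to 163 therefore follows exactly one miss, yet the table puts it in the row for two or more.

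**Step 4. First scan missed, progression at C5V1.** C5V1 falls 4 × 28 = 112 days after first dose, or 110 to 114 with ±2 days. Measured from treatment start, 113 and 114 exceed the limit: 2 of 5 possible days. The progression rows do not say that treatment start is the reference. Read literally, the last scan is then the baseline scan. Protocol 6.2.1 allows that scan up to 28 days before first dose. Censoring there would usually put the outcome before PFS time zero, which is first drug administration.

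**Step 5. What is unaffected.** With no missed scan the longest gap is 88 days, so no such patient is misclassified. Progressions found within 112 days at end-of-treatment or unscheduled scans are also unaffected.

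**The case against.** The strongest reply is that the SAP already gives an executable rule. The day limit makes the notion of a missed scan operational, and the progression-censoring row uses days alone. A programmer applying 112 days gets one answer once the reference date is known. A fixed limit also bounds unobserved time equally for everyone. Further, 12-weekly imaging is exceptional, and the 8-weekly mismatch rests on a borrowed visit window.

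Much of this stands as a limit on size. It does not remove the fault. The rule as executed contradicts the criterion it claims to express, and a progression scan one day late can be turned into a censoring at the previous scan. If a fixed bound on unobserved time is intended, the table should say so and drop the missed-scan wording.

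Three stronger readings are tempting but not supported:

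- *That nearly every progression after a missed first scan is censored.* Measured from a baseline scan 0 to 28 days before dosing, the gap would be 110 to 142 days, with 139 of 145 combinations above 112. That reading usually gives a negative PFS time and does not fit the table's other rows, which use treatment start. What remains is a missing clause.
- *That responders with two misses are counted as events.* This needs the confirmatory scan to count as scheduled and the 8-week grid to continue from the response scan. Missing the confirmatory and next scans then gives 108 to 116 days, with 15 of 25 pairs at or below 112. If the 8 weeks restart after confirmation, the nominal gap is 28 + 112 = 140 to 42 + 112 = 154 days, and words and days agree. The SAP settles neither assumption.
- *That late deaths off treatment are wrongly censored by the same mismatch.* Whether imaging continues after treatment is a separate conflict between footnote 13 and the Flow Chart with protocol 3.3.4.1.

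**Conclusion.** The point holds. The stated equivalence is false for the permitted 12-weekly imaging. There, a progression at the next scan after one miss, or a death on days 113 to 163, is treated as if two scans had been missed. The nominal 168-day case needs no assumption; the exact day ranges use ±2 days. On 8-weekly imaging the mismatch is confined to gaps of 113 to 116 days and depends on that window applying to scans. The missing reference date in the progression rows is a small but real gap.

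The consequence is limited to PFS and to DoR, which SAP 7.5.2 estimates only with at least 5 responders. Both are secondary, and protocol 7.2 plans no hypothesis test. Objective response, the primary endpoint of this part, is unaffected. A reader might infer a material bias in PFS, but the documents do not say how many patients will move to 12-weekly imaging or miss scans, so the effect cannot be quantified.

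**What to change.** In SAP Table 5.2.2:1:

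1. Replace the fixed 112 days by two of the patient's own scheduled intervals plus the visit window. Between two windowed scans this is 2 × 56 + 4 = 116 days on 8-weekly imaging and 2 × 84 + 4 = 172 days on agreed 12-weekly imaging. From treatment start, where only the later scan moves, it is 112 + 2 = 114 days. One larger limit for everyone would not work, because 164 to 172 days means one miss on 12-weekly and two on 8-weekly imaging.
2. Add the treatment-start reference to the progression rows when there is no post-baseline scan, in both the condition and the outcome date, as the death rows already do.
3. State whether the confirmatory response scan counts as a scheduled assessment, and how the schedule runs after it.

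Separately, reconcile footnote 13 (imaging until progression) with the Flow Chart and protocol 3.3.4.1 on when imaging ends, so that no assessment is counted as missed when none was due.

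A PFS sensitivity analysis counting every documented progression and death is optional. It should state how subsequent anti-cancer therapy is handled.

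The cost is SAP wording and a little programming. Each patient's agreed imaging interval must be recorded and available to the analysis. Some events after long gaps will carry less precise dates.

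### The PFS progression rows lack the death rows' treatment-start fallback, so for a child who misses only the week-8 scan and progresses at week 16 the event row contradicts itself, and its day count censors the child before the first dose

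*SAP*

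**What the plan says.** SAP 5.2.2 defines PFS as "the duration of time from the date of first drug administration to the date of the first documented disease progression" or death, so time zero is the first dose. Table 5.2.2:1 then sets the outcomes.

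- **Progression, event row:** "Progressed according to radiological assessment. At most one missed radiological assessments, i.e. at most 112 days between progression and last assessment before progression". The outcome date is the scan that shows progression.
- **Progression, censored row:** "Progressed according to radiological assessment, i.e. longer than 112 days between progression and last assessment before progression". The outcome date is "Date of last radiological assessment before progression". Unlike the death-censoring row, this row does not mention two or more missed scans.
- **Death rows:** the same 112-day limit, with a fallback. The censoring row reads "longer than 112 days between death and last assessment (or treatment start date if no post-baseline assessments" and dates the outcome at first administration when there is no post-baseline scan. The death-event row has the same fallback for the day count.

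Protocol 6.2.1 accepts a baseline tumour assessment "within the allowed time window (within 28 days prior to start of treatment". Imaging is every 8 weeks (protocol Flow Chart, footnote 13), at visit 1 of courses 3, 5, 7 and so on (protocol 6.2.2).

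**The concern.** When a child's first post-baseline scan shows progression, the only scan before progression is the baseline scan, which normally precedes the first dose. The progression rows then start the 112-day clock earlier than the death rows would, by the baseline lead time. The limit is exactly two 8-week intervals, so even a short lead time uses up all the room for one missed scan. A documented progression can therefore become a censored record dated before time zero, although the same row says that one missed scan still leaves an event. Progression and death would run on different clocks for the same scan history. Whoever programs PFS would have to choose between the row's words and its day count, possibly with the data in view.

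**Working it through.** **Inputs.** Scan interval 8 weeks and course length 28 days (protocol Flow Chart). First dose on day 1. Baseline scan *d* days before the first dose, with *d* up to 28 (protocol 6.2.1). Visit deviation *w* from −2 to +2 days (Flow Chart, course 3 onwards).

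**The plan's own limit.** 2 × 8 × 7 = 112 days, which matches the table.

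**Scan days.** Course 3 visit 1 is day 1 + 2 × 28 = 57. Course 5 visit 1 is day 1 + 4 × 28 = 113, which is 112 days after the first dose.

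**Week-8 scan missed, progression at week 16, literal day count.** Gap = 112 + *d* + *w*. The child is censored if the gap exceeds 112, and the PFS time is then −*d* days. For an on-time scan (*w* = 0):

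| *d* | Gap (days) | Outcome by day count | PFS time (days) |
|---|---|---|---|
| 0 | 112 | event | 112 |
| 1 | 113 | censored | −1 |
| 7 | 119 | censored | −7 |
| 14 | 126 | censored | −14 |
| 28 | 140 | censored | −28 |

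Over *d* = 1 to 28 and *w* = −2 to +2, 137 of 140 timing combinations (97.9%) are censored. If a same-day baseline (*d* = 0) is included, it is 139 of 145 (95.9%). These are shares of a timing grid, not probabilities for patients.

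**Latest progression still counted as an event** when no earlier post-baseline scan exists is 112 − *d* days after the first dose: 111 for *d* = 1, 98 for *d* = 14 and 84 (week 12) for *d* = 28.

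**Death comparator.** With no post-baseline scan, a death 112 days after the first dose has a gap of 112 days from treatment start and is an event at 112 days.

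**Other rows.** The row for no post-baseline imaging does not apply, because the week-16 scan is post-baseline. The row for a missing baseline scan does not apply either. If the previous assessment is read as post-baseline only, the progression rows give no reference date for this child.

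**Direction of the effect (illustrative counts, assumed).** Of 38 children, 20 progress at week 8, 2 progress at week 16 after a missed first scan, and 16 progress later. The SAP does not say how a negative time is handled, but dropping it or setting it to the start both take the 2 children out of the risk set before week 8.

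- Week 8: (38 − 20)/38 = 18/38 = 47.4% becomes 16/36 = 44.4%.
- Week 16: 16/38 = 42.1% becomes 16/36 = 44.4%.

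**Effect of the fallback alone.** Counted from the first dose, the gap is 112 + *w*. Scans that are early or on time (110 to 112) become events. A scan 1 or 2 days late (113 or 114) is still censored, now at time zero, so the limit also needs a window allowance.

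**The case against.** The best reply is that the event row's opening words settle the matter: one scan was missed, so the child is an event, and the day count only glosses that condition. Other rows also point to first administration as the natural floor. This has force. A reader might infer that the plan definitely censors these children, and the documents do not support that. They support a contradiction inside one row, with an impossible date on one side of it. The gloss is, however, the part that a program can apply, and the censored row carries only the day count.

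A reader might also infer that PFS is overstated throughout. It is not: the sign changes, and SAP 7.5.2 reports estimates at each planned assessment, so week 8 is a reported figure too.

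Nor should a reader infer that children scanned on schedule are affected. Progression at week 8 with the earliest allowed baseline has a gap of 56 + 28 = 84 days, within the limit. A late first scan is usually safe as well: a day −14 baseline and a day 70 scan are 84 days apart. A mandated scan must be missed altogether or be very late. The protocol makes that less likely, since eligibility to continue is confirmed at each course and the end-of-treatment visit includes imaging. No missed-scan rate is given, so any count of lost events would be a guess.

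Finally, protocol 7.2 plans no hypothesis test, and PFS is secondary.

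**Conclusion.** The point holds as a defect of wording in a descriptive secondary endpoint. The progression rows omit a fallback that the adjacent death rows contain. For one missed first scan followed by progression at week 16, the event row's words give an event, while its day count leads to censoring up to 28 days before the PFS origin. This rests on the baseline scan preceding the first dose. A same-day baseline with an on-time or early week-16 scan escapes, as does a baseline 1 or 2 days before the first dose with a sufficiently early scan.

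Under the literal day count, Kaplan-Meier PFS is slightly low at week 8 and too high from week 16. The size cannot be derived from the documents. Objective response is unaffected. Duration of response borrows the same table, but a responder already has a post-baseline scan, so this gap does not arise there.

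**What to change.** In SAP Table 5.2.2:1:

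1. In both progression rows, count the 112 days as the death rows do, adding "or treatment start date if no post-baseline assessments" and limiting it to assessments before progression.
2. In the censored progression row, date the outcome at first treatment administration when there is no post-baseline scan before progression. Add the condition of two or more missed scans, to match the death-censoring row.
3. Allow for the ±2-day visit window, so that a week-16 scan after one missed scan counts as an event. Counted from the first dose, this needs 112 + 2 = 114 days. Two missed scans would put the next scan at 3 × 56 = 168 days, so the two situations stay well apart.
4. In the row for subsequent anti-cancer therapy before progression or death, use first administration as the floor for children with no post-baseline scan before the new therapy who later progress. The next row already covers therapy followed by death.

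The cost is a short SAP revision and the matching derivation code. No data collection, visit or sample-size change is needed.

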5.1.1.2 Secondary endpoints

In the dose finding part of this trial, the objective tumour response (OR) assessed by investigator assessment according to the institutional response evaluation criteria for the given tumour type will represent a secondary endpoint.

In the MTD expansion cohorts/Phase II part, progression free survival (PFS) and duration of objective response (DoR) will be secondary endpoints for efficacy. PFS is defined as the duration of time from the date of first treatment until the date of the first documented progression or death due to any cause. If a patient has not had an event, PFS will be censored at the date of last adequate tumour assessment. Duration of overall objective response (DoR) is defined only for those patients with a response (CR or PR) as the interval between the date of randomization and the earliest date of disease progression.

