7.3.1 Primary analyses

Dose finding part:

In order to determine the MTD, the number of patients with DLT deemed to be related to administration of afatinib will be assessed based upon the patients in dose finding part of the trial. (See [Table 4.1.4.1:2](#)). The advanced disease of the patients in this trial makes it possible that significant adverse events, including events that would qualify as DLT, will occur, but will not be caused by afatinib. The MTD will be determined as the highest dose at which no more than 1/6 patients experienced DLT considered related to afatinib. (See [Table 4.1.4.1:1](#))

Proprietary confidential information.

© 2017 Boehringer Ingelheim International GmbH or one or more of its affiliated companies. All rights reserved.

This document may not - in full or in part - be passed on, reproduced, published or otherwise used without prior written permission.

Pharmacokinetics is a primary endpoint for the dose finding part. For details see [Section 7.3.5](#)

MTD expansion cohorts/Phase II part:

OR will be assessed when the last patient enrolled in the MTD expansion cohorts/Phase II part will be evaluable for efficacy.

Each patient will be assigned to one of the following categories based on investigator's assessment according to the institutional response evaluation criteria for the given tumour type, irrespective of protocol violation or missing data:

- CR (complete response)
- PR (partial response)
- SD (stable disease)
- PD (progressive disease)
- Not evaluable (not assessable, insufficient data)

Objective response is defined as CR and PR.

If the International Criteria for Neuroblastoma Response Criteria (INRC) ([R14-2418](#)) is used, each patient will be assigned to one of the following categories:

- CR (complete response)
- VGPR (very good partial response)
- PR (partial response)
- MxR (mixed response)
- NoR (no response)
- PD (progressive disease)

The objective response is then defined as CR, VGPR, PR or MxR.

OR will be tabulated and provided with the proportion and the exact 95% confidence interval based on all treated patients in the MTD expansion cohorts/Phase II part.

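### SAP Table 5.2.2:1 censors PFS at the last radiological assessment, where the protocol requires the last adequate tumour assessment, and the SAP does not declare the change

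*SAP*

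**What the plan says.** Protocol section 5.1.1.2 gives the censoring rule in one sentence: "If a patient has not had an event, PFS will be censored at the date of last adequate tumour assessment".

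SAP section 5.2.2 says that censoring rules and outcome dates are specified in its Table 5.2.2:1. There the row "Alive and not progressed (irrespective of missed radiological assessments" is censored at the date of the last radiological assessment. The row for a death after two or more missed scans uses "Date of last radiological assessment / Date of first treatment administration if no post-baseline assessments". Two further rows also date the outcome at the last radiological assessment: progression found after a long gap, and subsequent anti-cancer therapy started first. None of these four rows asks that the assessment be adequate or evaluable.

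The table also uses the last assessment to decide whether a late death or progression is an event. For deaths, the row reads "At most one missed radiological assessments, i.e. at most 112 days between death and last assessment". DoR follows the same rules.

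Below the table the SAP adds: "For further details on endpoints, please see CTP Section 5". SAP section 4 corrects the protocol's DoR definition but says nothing about the PFS censoring date. The SAP history table records that the 14 July 2020 revision added the PFS censoring rules and aligned endpoint definitions with the protocol.

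**The concern.** A scan that cannot be evaluated is no evidence that the child is free of progression. If it sets the censoring date, the child stays in the risk set for a further interval without information.

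The plan foresees such assessments. Protocol section 7.3.1 has the patient-level category "Not evaluable (not assessable, insufficient data", and SAP Table 7.4.2:1 has a time-point category that groups non-evaluable with missing. The PFS table has no corresponding rule. At stake are the Kaplan-Meier PFS estimates at each planned assessment, in at most 38 expansion patients, and the DoR estimates where these are produced. If the plan is left as it is, the analyst must choose between two written rules, possibly after seeing the data.

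**Working it through.** **Inputs from the documents.** Imaging "is to be performed every 8 weeks until progression of disease" (protocol flow chart, footnote 13). Gap limit 112 days (SAP Table 5.2.2:1). Up to 38 expansion patients (protocol synopsis). PFS by Kaplan-Meier with no hypothesis test (SAP 7.5.2, protocol 7.2).

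**The plan's own figure.** 2 × 8 weeks × 7 days = 112 days. It reproduces.

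**Kaplan-Meier formula.** S(t) is the product of (1 − d/n) over event times up to t. Moving a censoring date later leaves d unchanged and raises n at event times between the two dates. Taken alone, it can therefore only raise the curve or leave it unchanged.

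**Example 1: the curve moves.** Patient A has an evaluable scan on day 56, a non-evaluable scan on day 112 and nothing later. Five others progress on days 56, 112, 112, 168 and 168.
- SAP wording, A censored on day 112: S(112) = 5/6 × 3/5 = 0.500.
- Protocol wording, A censored on day 56: S(112) = 5/6 × 2/4 = 0.417.
- The median is 112 days either way.

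**Example 2: no change.** The others progress on days 56, 168, 168, 168 and 224, so no event falls between A's two possible dates. Both rules give S(168) = 5/6 × 1/4 = 0.208.

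**Example 3: the gap rule.** A has the same two scans, then dies on day 200. The others progress on days 56, 112, 112, 168 and 224.
- Counting any scan: the gap is 200 − 112 = 88 days, within 112, so A has an event on day 200.
- Counting evaluable scans only: the gap is 200 − 56 = 144 days, over 112, so A is censored on day 56.

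| Day | Any scan | Evaluable scan |
|---|---|---|
| 112 | 0.500 | 0.417 |
| 168 | 0.333 | 0.208 |
| 200 | 0.167 | 0.208 |

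Here the any-scan reading is higher early and lower late.

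**Simulation.** N = 38, 8-weekly scans, 1000 runs in each of 18 settings. None of the following assumptions comes from the documents:
- median time to progression 60, 120 or 240 days;
- 5%, 10% or 20% of scans non-evaluable, independent of progression;
- median time to stopping scans 120 or 365 days, with a cut-off between 180 and 730 days;
- median 90 days from progression to death.

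Each reading was applied to both the censoring date and the 112-day rule, so the results combine the two effects. The figures below are any-scan minus evaluable-scan, as ranges over settings.

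| Non-evaluable rate | Mean change in 24-week PFS (points) | Trials higher | Trials lower | Extra events per trial |
|---|---|---|---|---|
| 5% | +0.14 to +0.43 | 22–51% | 3–6% | 0.12–0.18 |
| 10% | +0.24 to +0.87 | 36–69% | 8–15% | 0.24–0.49 |
| 20% | +0.61 to +1.99 | 65–75% | 21–23% | 0.74–1.45 |

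Across all settings the outermost 2.5th and 97.5th percentiles were −4.6 and +8.7 points. The mean shift in median PFS ran from −3.4 to +6.1 days.

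**Scale.** At an assumed PFS of 30% without censoring, the 95% half-width for 38 patients is 1.96 × √(0.3 × 0.7 / 38) = 14.6 points.

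**The case against.** The best defence is that the SAP does not say a non-evaluable scan counts. The table is silent, the SAP describes itself as an elaboration of the protocol analysis, section 4 declares no change to PFS censoring, and the pointer under the table leads to the protocol section that holds the adequacy rule. Where the SAP does deal with non-evaluable time points, for response confirmation, it treats them like missing ones. The sponsor may well intend the protocol rule.

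That is fair as to intent. It does not settle the text. The SAP says its table specifies the rules and dates, the pointer is general, and a non-evaluable scan is still a radiological assessment in ordinary words. The two documents can give different dates for the same child.

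Two further objections stand. The protocol does not define *adequate*, so reading it as *evaluable* is an inference. And PFS is secondary and untested, while further development is to be judged on objective response. With fewer than 5 responders, DoR is only listed.

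A reader might infer that reported PFS will be overstated. The documents do not support that. Example 2 shows no effect, and through the 112-day rows a counted non-evaluable scan can add events and lower late PFS. Larger shifts can be obtained by assumption: 1.8 to 7.5 points at weeks 16 and 24 if scans are three times as likely to be non-evaluable after true progression and half of patients leave imaging after such a scan. The documents support neither input.

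**Conclusion.** The point holds as an undeclared conflict between the protocol and the SAP on the PFS censoring date. Read literally, the SAP allows a non-evaluable scan to extend progression-free follow-up, for example from day 56 to day 112.

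The likely effect is small: a mean rise of about 0 to 2 points in 24-week PFS under assumed non-evaluable rates of 5% to 20%, against a confidence half-width near 15 points. Direction varies by trial once the 112-day rule is included. The simulation does not separate the two effects, and the true non-evaluable rate is unknown. No alpha, power or sample size figure changes. The case for acting is that the correction is nearly free and removes a choice that could otherwise be made after the data are seen.

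The 112-day rows are a separate open question and no part of the upward tendency claimed here. A reader might conclude that non-evaluable scans should simply be treated as missed there. Protocol 5.1.1.2 does not require that: it counts death from any cause with no gap limit, and in Example 3 that treatment would discard a real death.

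**What to change.** In the four rows of SAP Table 5.2.2:1 whose outcome date is the last radiological assessment, write last adequate (evaluable) tumour assessment, and define it once as an assessment with an evaluable overall response. Let the existing fallback to the first treatment date cover patients with no adequate post-baseline assessment. Apply the same wording to DoR where it is estimated. If the sponsor prefers the present wording, declare the departure in SAP section 4 with a reason.

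Separately, state before database lock whether a non-evaluable scan counts as an assessment in the 112-day gap rows. That choice can move events in either direction, so it should be made deliberately.

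The cost is a sentence in the SAP and one condition in the derivation. With the gap rule held fixed, the date change can only lower the PFS curve or leave it as it is, so reported PFS may be slightly less favourable.
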